4.6.5.2. Lymphocyte Subset Cell Counts

The following lymphocyte subsets will be analyzed:

CD3+ T Cells – %

CD3+ T Cells – Absolute

CD3+CD8+ T cells (CD8) – %

CD3+CD8+ T cells (CD8) – Absolute

CD3+CD4+ T cells (CD4) – %

CD3+CD4+ T cells (CD4) – Absolute

CD56+/CD16+ NK cells – %

CD56+/CD16+ NK cells – Absolute

CD19+ B cells – %

CD19+ B cells – Absolute

CD4/CD8 Ratio – Calculated

CD3+4+8+ %

CD3+4+8+ Abs

CD3/CD19 Ratio - Calculated

For each type of cells, both the absolute count and the relative count (i.e., as a percentage of the total lymphocyte population) will be analyzed. In addition, the ratio of CD4 cell counts to CD8 cell counts will be analyzed.

The analyses for these parameters will be performed using the same approaches as described for analysis of clinical laboratory measurements in Section 4.6.5. For determining treatment-emergent abnormal, high, or low lymphocyte subset cell counts, central laboratory reference ranges (Labcorp) will be used when available; note that reference ranges are available only for some of the lymphocyte subset cell count analytes.

4.6.5.3. Lipids Effects

Analyses for the change from baseline to last observation, and shift tables in total cholesterol, LDL cholesterol, HDL cholesterol, and triglycerides are described in Section 4.6.5.

Treatment-emergent adverse events potentially related to hyperlipidemia will also be analyzed, based on reported AEs. The target surveillance term “Hyperlipidemia” is a Lilly-defined MedDRA search criteria list that is a subset of the PTs in the MedDRA SMQ “Dyslipidemia” that are related to elevated or increased lipids. MedDRA PTs, each with a narrow scope from the SMQ, for the target surveillance term are shown in 6.9. Frequency and relative frequency for each PT will be provided, ordered by decreasing frequency in the LY3471851 1800µg treatment group.

4.6.5.4. Renal Function Effects

Effects on renal function will be assessed through analyses of creatinine, which are described in Section 4.6.5.

4.6.5.5. Elevations in Creatine Phosphokinase

Analyses of creatine phosphokinase are described in Section 4.6.5.

4.6.5.6. Serum Immunoglobulin Concentrations

Each serum Ig concentration (IgA, IgG, and IgM) will be analyzed. The analyses for these parameters will be performed using the same approaches as described for analysis of clinical laboratory measurements in Section 4.6.5. For determining treatment-emergent abnormal, high, or low serum Ig concentrations for IgA, IgG, and IgM, central laboratory reference ranges (Labcorp) will be used.

4.6.6. Vital Signs and Other Physical Characteristics

Vital signs and physical characteristics include systolic blood pressure (SBP), diastolic blood pressure (DBP), pulse, weight, BMI, and body temperature. Original-scale data will be analyzed. When these parameters are analyzed as continuous numerical variables, unplanned measurements will be excluded. When these parameters are analyzed as categorical outcomes, planned and unplanned measurements will be included.

Vital signs and physical characteristics will be summarized and analyzed for the following periods:

- Induction Period

- Maintenance Period
- Extension Period

The planned analyses described for the laboratory analytes in Section 4.6.5 will be used to analyze the vital signs and physical characteristics.

Table KFAH.5 defines the low and high baseline values as well as the criteria used to define treatment-emergence based on postbaseline values. Postbaseline values include all values after baseline in the treatment and follow-up periods. The blood pressure and pulse rate criteria are consistent with the document *Selected Reference Limits for Blood Pressure, Orthostasis, and ECG Numerical Parameters (Including Heart Rate) for Use in Phase II-IV Clinical Trials Version 1.1* approved on 8 March 2013 as recommended by the Lilly Cardiovascular Safety Advisory Committee (CVSAC).

Table KFAH.5. Categorical Criteria for Abnormal Treatment-Emergent Blood Pressure and Pulse Measurement, and Categorical Criteria for Weight Changes for Adults

	Low	High
Systolic Blood Pressure (mm Hg)	≤ 90 (low limit) and decrease from lowest value during baseline ≥ 20 if > 90 at each baseline visit	≥ 140 (high limit) and increase from highest value during baseline ≥ 20 if < 140 at each baseline visit
Diastolic Blood Pressure (mm Hg)	≤ 50 (low limit) and decrease from lowest value during baseline ≥ 10 if > 50 at each baseline visit	≥ 90 (high limit) and increase from highest value during baseline ≥ 10 if < 90 at each baseline visit
Pulse (beats per minute)	< 50 (low limit) and decrease from lowest value during baseline ≥ 15 if ≥ 50 at each baseline visit	> 100 (high limit) and increase from highest value during baseline ≥ 15 if ≤ 100 at each baseline visit
Weight (kilograms)	(Loss) decrease $\geq 7\%$ from lowest value during baseline	(Gain) increase $\geq 7\%$ from highest value during baseline

[figure not shown]
Abbreviation: mm Hg = millimeters of mercury.

4.6.7. Electrocardiograms

Detailed Electrocardiogram results are part of the clinical database for this study. Should an ECG be performed in association with an AE or medical history event, the occurrence of the ECG (“Yes/No”) will be provided in a by-patient listing.

If any clinically significant ECG measurement occurs, this will be recorded as an AE. ECG data will not be analyzed.

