9.4.4. Safety Analyses

Safety analyses will include AEs, SAEs, AESIs, C-SSRS, QIDS-SR16, vital signs, ECGs, and laboratory analytes, using the Safety Population data descriptively summarized by treatment group. Categorical safety measures will be summarized with incidence rates. Continuous safety measures will be summarized as mean change by visit. Exposure to study intervention will be calculated for each participant and summarized by treatment group.

Adverse events will be coded according to MedDRA and summarized by system organ class, preferred term, severity, and relationship to the study intervention. A TEAE is defined as an event that first occurred or worsened in severity after baseline, with baseline defined as all pre-existing conditions recorded at Visit 1 and any AEs recorded before the first dose of study intervention (that is, during the interval between Visits 1 and 2, and recorded with the time of onset before the first dose of study intervention). The treatment period will be used as the postbaseline period for the analysis. For events that are gender specific, the denominator and computation of the percentage will include only participants from the given gender.

The number and percentage of participants who experienced TEAEs, TEAEs by maximum severity, deaths, SAEs, TEAEs related to study intervention, discontinuations from the treatment due to an AE, and AESIs will be summarized. Treatment-emergent adverse events (all, by

maximum severity), SAEs including deaths, and AEs that lead to treatment discontinuation will be summarized and analyzed by MedDRA SOC and preferred term.

Treatment-related TEAEs (TEAEs related to study intervention) are defined as events that are indicated by the investigator on the eCRF to be related to treatment.

Adverse events of special interest will be identified by a standardized MedDRA query (SMQ) or a Lilly-defined MedDRA preferred term listing.

Follow-up emergent AEs, SAEs including deaths, and AEs that lead to study discontinuation will be summarized. All AEs, including pre-existing conditions, will be listed by participant, visit, preferred term, treatment group, severity, and relationship to the treatment.

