4.5. Tertiary/Exploratory Endpoints Analyses

4.6. Safety Analyses

All safety data will be descriptively summarized by treatment groups and analyzed based on the safety population as defined in Section 3. The safety analyses include AEs, safety in special groups and circumstances, including Adverse Events of Special Interest (AESI), laboratory analytes, QIDS-SR16, C-SSRS, ECGs, and vital signs. The duration of exposure will also be summarized. The categorical safety measures will be summarized using incidence rates and analyzed by Fisher's exact test. The mean change in the continuous safety measures including vital signs, QIDS-SR16, physical characteristics, and laboratory values will be summarized by visits and analyzed by ANCOVA, with treatment and baseline values in the model. More details are provided in subsequent sections.

For specific events of special interest (see Section 4.6.3 for more details), an incidence rate, IR per 100 patient-years of observation (PYO), will be provided. Patient-years of observation will be calculated as the sum of all patient observation time in the treatment group. For a patient with an event, the observation time will be censored at the event date; for a patient without the event, the observation time will be counted until the patient's last treatment dose date plus 30 days or the patient's last visit, whichever occurs first. Only events that occur within 30 days after the patient's treatment discontinuation date will be considered.

See formula as follows:

$$\begin{aligned}
 PYO = & \sum_{pt \ w \ event} \frac{event \ start \ date - first \ trt \ dose \ date + 1}{365.25} \\
 & + \sum_{pt \ w/o \ event} \frac{last \ observation \ date - first \ trt \ dose \ date + 1}{365.25}
 \end{aligned}$$

Incidence rate will be calculated as follows:

$$IR = \frac{\text{unique number of patients with event}}{PYO} \times 100$$

For each IR provided, a 95% CI will be calculated based on the Poisson distribution. Treatment group comparisons based on IR will be provided based on the incidence rate difference (IRD) together with its 95% CI.

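### SAP 4.6.7 drops the ECG analysis that protocol 9.4.4 and SAP 4.6 promise, without declaring the change, so ECG intervals are never summarised by treatment group

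*SAP*

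**What the plan says.** Protocol 9.4.4 sets the scope: "Safety analyses will include AEs, SAEs, AESIs, C-SSRS, QIDS-SR16, vital signs, ECGs, and laboratory analytes", "using the Safety Population data descriptively summarized by treatment group". It adds general rules, under which categorical safety measures are reported as incidence rates and continuous ones as mean change by visit.

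SAP 4.6 repeats the commitment. It opens with "All safety data will be descriptively summarized by treatment groups", and its list of what the safety analyses include contains "laboratory analytes, QIDS-SR16, C-SSRS, ECGs, and vital signs".

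SAP 4.6.7 then makes four statements:

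- On the data: "Detailed Electrocardiogram results are part of the clinical database for this study".
- On output, for an ECG done in connection with an adverse event or a medical history event: "the occurrence of the ECG (“Yes/No”) will be provided in a by-patient listing".
- On individual findings: "If any clinically significant ECG measurement occurs, this will be recorded as an AE".
- On analysis: "ECG data will not be analyzed".

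SAP section 1 states that the protocol's analyses are unchanged. SAP 4.9, whose heading promises changes to protocol-planned analyses, deals only with important protocol deviations. Protocol 9.4.1 requires a change of method that does not alter a principal feature to be described and justified in the SAP and the clinical study report.

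**The concern.** A programmer cannot follow SAP 4.6 and SAP 4.6.7 together, and a reader of the protocol would expect ECG tables that the SAP does not plan. The departure is neither declared nor explained.

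What would be lost is the by-arm view of ECG intervals and abnormality categories. The drug is a PEG-conjugated IL-2, and protocol 2.3 names cardiac rhythm disturbances among the effects known with high-dose IL-2 (aldesleukin). Protocol 8.2.3 names change from baseline in QT/QTc as an example of a finding that may be clinically significant. Review of one participant at a time can pick up a large individual change. It is poorly placed to show a small shift across a whole arm, which needs a summary against concurrent placebo.

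**Working it through.** The plan gives no statistical figure to reproduce. The check is a comparison of texts and a count of scheduled tracings.

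**1. The commitments side by side**

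| Place | ECGs named as a safety analysis? | Planned form |
|---|---|---|
| Protocol 9.4.4 | Yes | Descriptive summary by treatment group |
| SAP 4.6 | Yes | Descriptive summary by treatment group |
| SAP 4.6.7 | No | Yes/No listing for event-related ECGs only |
| SAP 1 | – | Declares no change from the protocol |
| SAP 4.9 | – | Declares no ECG change |

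Rows 1 and 2 conflict with row 3, and row 3 makes row 4 untrue for ECGs.

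**2. What is scheduled (protocol 1.3, Tables 1 to 4)**

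- Everyone: V1 (screening) and V9 (Week 12).
- Week 12 responders: V15 (Week 24) and V29 (Week 52).
- Week 12 nonresponders: V10 (Week 14), V16 (Week 26), V22 (Week 38) and V29 (Week 52).
- Early termination: one ECG at the ETV.

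A responder who completes has 2 + 2 = 4 ECGs, 3 of them after baseline. A nonresponder who completes has 2 + 4 = 6, 5 of them after baseline.

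For scale only, take the planned total of about 200 participants and assume that all complete. If all were responders, there would be 200 × 3 = 600 post-baseline ECGs; if all were nonresponders, 200 × 5 = 1,000. Early discontinuation, including the planned stop for Week 26 nonresponders, would lower both figures.

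**3. How a scheduled ECG can reach a safety result**

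- A finding judged clinically relevant is reported as an adverse event (protocol 8.2.3, SAP 4.6.7). If treatment-emergent, it is tabulated by treatment group (SAP 4.6.2.1).
- Heart rate is covered in substance by pulse, which is measured at every scheduled treatment visit. SAP 4.6.6 analyses it by the laboratory methods of 4.6.5: change from baseline, an ANCOVA p-value, and treatment-emergent high and low values by Fisher's exact test. Table KFAH.5 supplies the pulse limits.
- Interval values and ECG abnormality categories have no route other than the adverse event.

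**4. Where a placebo comparison is cleanest**

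Week 12 is the only post-baseline visit with a scheduled ECG for all participants still on randomised treatment. After that, protocol 4.1 moves nonresponders to LY3471851, and placebo remains only among Week 12 responders.

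**The case against.** A reader might infer that the scheduled ECGs contribute nothing to the safety evaluation. The documents do not support that. A qualified physician reads each tracing, QT/QTc change from baseline is expressly within that review, the medical monitor is involved when a significant finding arises after enrolment, and new clinically relevant findings become adverse events that reach the by-arm tables. ECGs also serve eligibility and participant management.

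A reader might also infer that a change in heart rate against placebo would go unseen. It would not, because pulse is analysed by arm.

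Nor do the documents point to an existing cardiac signal. The sentence in protocol 2.3 that names rhythm disturbances with high-dose IL-2 reports no evidence of such events in the Phase 1 studies of this drug, and cardiac events are not among the adverse events of special interest in protocol 8.3.6.

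Two further objections carry weight. First, protocol 9.4.4 sets no ECG parameters or limits, so detailed tables of values outside limits for each period would go beyond what it promises. Second, it is not certain that interval values are held. The ECGs are performed locally, neither document describes central reading, and a Yes/No listing sits oddly beside a claim of detailed results. The database sentence may itself be the drafting error.

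These objections narrow the consequence and add a condition to the remedy. They do not remove the contradiction or supply the missing justification.

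**Conclusion.** The contradiction is confirmed from the text: SAP 4.6.7 conflicts with protocol 9.4.4 and SAP 4.6, and it falsifies the no-change statement in SAP section 1. The consequence is limited. ECG data reach the safety results only through investigator-reported adverse events, so a modest group-level shift in intervals that no reader called clinically significant would appear in no planned output.

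The number of findings affected cannot be derived from the documents; only the 3 to 5 post-baseline tracings per completer can. The primary and secondary efficacy analyses and the power statement are untouched, so this is a minor point. The loss of information rests on one assumption, that the database holds interval values as SAP 4.6.7 says. The inconsistency needs correcting whether or not that is so.

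**What to change.** First confirm which ECG variables are in the clinical database.

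**If interval values are held:** replace the last sentence of SAP 4.6.7 with the descriptive summary that the protocol promises. Give mean change from baseline in the recorded ECG parameters by visit and treatment group, and the incidence of abnormal findings by treatment group, on the Safety Population. The cost is one or two extra tables from data already collected.

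**If they are not held:** correct the database sentence in SAP 4.6.7, remove ECGs from the list in SAP 4.6, amend the no-change statement in SAP section 1, and declare and justify the departure from protocol 9.4.4 in SAP 4.9 and the clinical study report. This costs a few lines of text. If the sponsor regards the change as leaving the protocol's principal features intact, protocol 9.4.1 requires no amendment.

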4.6.9. Suicidal Ideation/Behavior and Depression

During the study, suicidal ideation and behavior, and depression will be assessed prospectively by the investigator via signs and symptoms and through the use of the Columbia-Suicide Severity Rating Scale (C-SSRS) and the Quick Inventory of Depressive Symptomatology Self Report (QIDS-SR16).

Analyses will include:

- C-SSRS: Only a listing of the C-SSRS data will be provided.
- QIDS-SR16: Shift table will be provided showing the number and percentage of patients within each baseline category (maximum value) versus each post-baseline category (maximum value) by treatment. Additionally, outcomes such as any increase in depression will be compared between treatments.

4.7. Other Analyses

4.7.1. Efficacy Subgroup Analysis

Subgroup analyses will be conducted on the mITT population for the following:

- Clinical remission
- Clinical response
- Endoscopic remission
- Endoscopic response
- Symptomatic remission
- Symptomatic response
- Histologic remission
- Histologic-endoscopic mucosal healing

The following subgroups (but not limited to only these) will be evaluated:

- Gender
- Age category
- Body weight
- Race
- Geographic region
- Baseline disease severity and activity
- Duration and location of disease

- Previous systemic therapy
- Previous advanced therapy, and
- Concomitant therapy for UC.

Descriptive statistics will be provided for each treatment and stratum of a subgroup as outlined, regardless sample size.

Each categorical variable will be analyzed individually with a logistic regression model that contains the treatment, the subgroup variable, and subgroup by treatment interaction. The treatment-by-subgroup interaction will be tested at the 10% significant level. Within each subgroup category, the proportion of responders by treatment, treatment differences, and 95% CIs will be displayed.

For continuous variables, MMRM analysis will be performed with subgroup-by-treatment interaction. Within each subgroup, LS means by treatment, LS mean differences, and 95% CIs will be displayed.

If the number of patients in any subgroup category is less than 10% of the total population, only summaries of the efficacy data will be provided. Additional subgroup analyses may be performed as deemed necessary.

4.7.2. Safety Subgroup Analyses

Safety subgroup analysis for safety related endpoints will be performed within the context of the integrated safety analysis. No safety subgroup analysis will be performed specifically for this study unless there is a potentially relevant finding during the periodic study safety reviews.

4.8. Interim Analyses

Analyses for the primary database lock will be conducted when all participants have completed the Induction Period (that is, have completed the Week 12 visit) or else have discontinued study treatment.

The following interim analyses may be conducted to assess the primary efficacy results:

- for early termination assessment and decision when approximately 50 patients have either completed the dosing induction period or discontinued study treatment,
- for early termination or Stage 2 dose decisions when approximately 100 patients have either completed the dosing induction period or discontinued study treatment,
- for early trigger to Phase 3 assessment when approximately 150 patients have either completed the dosing induction period or discontinued study treatment, and
- for Phase 3 study trigger when approximately 200 patients have either completed the dosing induction period or discontinued study treatment.

Bayesian pairwise comparisons (LY3471851 dose to placebo) will be employed for potential decisions at each interim analysis using Bayesian posterior probability. Note that Stage 2 treatment doses will be determined based on results of the second interim analysis and recommendations of the sponsor's IAC.

The interim efficacy results will be used for internal decision making to terminate or trigger planning activities associated with the investigational product and to aid development of PK/PD modeling. Hence, there will be no alpha adjustment at the interim analyses. For each pairwise comparison at each interim analysis, a alpha of 0.05 will be used. The study may not be stopped for positive efficacy. The assessment will be conducted by a sponsor assessment committee with a limited number of pre-identified team members who do not have direct site contact or data entry/validation responsibilities. To minimize any bias being introduced into the analysis of the study results, the SAP and PK/PD analysis plan will be finalized and approved before the first efficacy interim analysis is initiated.

Information that may unblind the study during the analyses will not be reported to study sites or the blinded study team until a decision is made to unblind the entire study team.

Ongoing monitoring of safety data (including AEs, SAEs, and selected laboratory measurements) will be continued throughout the study using blinded data. Reviewing details are specified in the trial level safety review (TLSR) plan or a separate document.

4.8.1. Data Monitoring Committee (DMC)

Not applicable. An assessment of unblinded interim data will be conducted by an internal assessment committee (IAC) with a limited number of prespecified team members who do not have direct site contact or data entry or validation responsibilities. An AC charter will provide details on AC membership and the governing processes.

4.9. Changes to Protocol-Planned Analyses

Protocol deviations will be identified throughout the study. Important protocol deviations (IPDs) are defined as those deviations from the protocol that would potentially compromise patients' safety, data integrity, or study outcome.

A separate document known as the "The KFAH Trial Issues Management Plan" describes the categories and subcategories of important protocol deviations, whether or not these deviations are IPDPPs, and how the IPDs would be identified.

The number and percentage of patients having IPDs will be summarized within category and subcategory of deviations by dosing regimen for the mITT population.

5. Sample Size Determination

Approximately 200 participants, in total, may be randomized across all study stages.

During Stage 1, approximately 100 participants will be randomized to a high dose (CC1 μg) of LY3471851, a lower (CC1 μg) dose of LY3471851, or placebo groups in a 2:2:1 ratio.

During Stage 2, up to approximately 100 additional participants will be randomized. Stage 2 will have a placebo group and may have more LY3471851 treatment groups than Stage 1, or fewer, based on decisions taken after the last interim analysis of Stage 1.

The power calculations for this study assume the following:

- At end of study, three non-placebo treatment groups will have sample size of approximately either 40, 60, or 80 patients.
- At end of study, the placebo group will have a sample size of approximately 40 patients.
- For the sake of simplicity in the power calculation, it is assumed that there is no difference in treatment effect between advanced therapy-failed and conventional-failed patients. To simplify, it is also assumed that all treatment groups have the same treatment effect.
- It is assumed that the true placebo response rate is approximately 5% and the true treatment response is approximately 35%.
- Power is calculated for 3 hypothesis tests, 1 for each treatment group against placebo, and adjust for multiple comparisons using the conservative Bonferroni adjustment. Power is calculated using a family-wise error rate of $\alpha=.05$.

Given these assumptions, the power to reject the null hypotheses for the treatment groups with sample sizes equal to 40, 60, and 80 are 89.5%, 94.5%, and 96.5%, respectively. As an example, in a fixed design, with the placebo and LY3471851 treatment groups each having 80 participants, a 17% or larger difference between the groups can be detected with 90% power and assuming a 5% placebo effect.

6. Supporting Documentation

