9.2. Sample Size Determination

Approximately 200 total participants, in total, may be randomized across all study stages.

- During Stage 1, approximately 100 participants will be randomized to 1 of 3 treatment groups in a 2:2:1 ratio:
 - a high dose (CC1 μ g) of LY3471851
 - a lower (CC1 μ g) dose of LY3471851, or
 - placebo.
- During Stage 2, up to approximately 100 additional participants will be randomized. As stated in Section 4.1, Stage 2 will have a placebo group and may have more LY3471851 treatment groups than Stage 1, or fewer, based on decisions taken after the last interim analysis of Stage 1. The randomization ratio for Stage 2 will be determined and documented as part of the decision-making about the number of treatment groups. This decision making will occur following Stage 1, and the choice in allocation ratio may be adjusted to achieve the planned allocation across treatment arms.

The power calculations for this study assume the following:

- At end of study, three non-placebo treatment groups will have sample size of approximately either 40, 60, or 80 patients.
- At end of study, the placebo group will have a sample size of approximately 40.
- For the sake of simplicity in the power calculation, it is assumed that there is no difference in treatment effect between advanced therapy-failed and conventional-failed patients. To simplify, it is also assumed that all treatment groups have the same treatment effect.
- It is assumed that the true placebo response rate is approximately 5% and the true treatment response is approximately 35%.
- Power is calculated for 3 tests, 1 for each treatment group against placebo, and adjusted for multiple comparisons using the conservative Bonferroni adjustment. Power is calculated using a family-wise error rate of $\alpha=.05$.

Given these assumptions, the power to reject the null hypotheses for the treatment groups with sample sizes equal to 40, 60, and 80 are 89.5%, 94.5%, and 96.5%, respectively. As an example, in a fixed design, with the placebo and LY3471851 treatment groups each having 80 participants, a 17% or larger difference between the groups can be detected with 90% power and assuming a 5% placebo effect.

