9.4. Statistical Analyses

9.4.1. General Considerations

Statistical analysis of this study will be the responsibility of Lilly or its designee.

Efficacy analyses will be conducted on the mITT population. Safety analyses will be conducted on the mITT population (Safety Population). The efficacy analysis of the primary endpoint and secondary endpoints will be repeated for ITT population. Additional safety analyses may be performed as deemed appropriate.

The baseline MMS is calculated from valid daily diary entries obtained prior to endoscopy during the screening period and the endoscopic appearance of the mucosa at this screening endoscopy. For other efficacy, health outcome and safety assessments, baseline is defined as the last non-missing assessment recorded on or prior to the date of the randomization visit (Visit 2).

Summary statistics for continuous variables may include mean, standard deviation, median, and minimum and maximum values. Categorical variables will be presented as counts and percentages. Unless otherwise specified, variables will be analyzed in the original scale on which they are measured. The parametric approach will be employed by default for statistical analysis except when nonparametric analysis, such as by a rank-based method, is considered to be more fitting. Additional exploratory analyses of the data will be conducted as deemed appropriate.

Unless otherwise specified, analysis of hypotheses will be tested without multiplicity control at a significance level of 0.05. A 2-sided 95% CI will be provided along with the p-value. For other analyses, statistical tests without multiplicity control will be conducted using a 2-sided significance level of 0.05. The corresponding p-value along with its 95% 2-sided CI will be provided. Additional analyses may also include subgroup analyses for the primary and the secondary endpoints.

For assessments of the primary endpoint and other categorical efficacy endpoints, the CMH chi-square test will be used to compare the treatment groups with the following factors:

- previous advanced therapy failure status (yes/no)
- baseline corticosteroid use (yes/no)
- baseline disease activity (MMS: [4 to 6] or [7 to 9]), and
- region (North America/Europe/Other).

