9.4.1.3. Adjustment for Multiple Comparisons

Adjustment for multiple comparisons will not be employed in the analysis for this study.

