2.1. Multiplicity Adjustment

Multiplicity adjustment will not be employed in the analysis for this study.

3. Analysis Sets

Table KFAH.2 describes the populations planned for use in the analyses. The mITT population, as defined below, will be used in analyses of efficacy and PRO, unless otherwise noted in the SAP.

Table KFAH.2. Analysis Populations

Population	Description
ITT Population	All randomized participants. Participants will be analyzed according to the treatment to which they were assigned.
mITT Population	All randomized participants who receive at least 1 dose of study treatment (regardless of whether the participant fails to receive the correct treatment, or otherwise fails to follow the protocol). Participants will be analyzed according to the treatment to which they were assigned.
Safety Population	Same as mITT population
Pharmacokinetic Evaluable	All participants who receive at least 1 dose of investigational product and have sufficient blood sampling to allow for pharmacokinetic evaluation.

Abbreviations: GCP = Good Clinical Practice; ITT = intent-to-treat; mITT = modified intent-to-treat; SAP = statistical analysis plan.

Analyses of the maintenance dosing period and the extension periods will be based on the corresponding enrolled population as described in the table above.

4. Statistical Analyses

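### The stated power uses a Bonferroni alpha that the analysis does not use, and the 17-point example names no alpha and assumes twice the planned placebo group.

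*SAP*

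**What the plan says.** Protocol 9.2 and SAP Section 5 carry the same power paragraph. It assumes remission rates of 5% on placebo and 35% on active drug, and active groups of about 40, 60 or 80. For placebo: "At end of study, the placebo group will have a sample size of approximately 40 patients". Power is for three tests, one per dose against placebo, with family-wise error 0.05. The protocol has these "adjusted for multiple comparisons using the conservative Bonferroni adjustment" and the SAP says "adjust for multiple comparisons using the conservative Bonferroni adjustment". The result is 89.5%, 94.5% and 96.5%.

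A fixed-design example follows at once, "with the placebo and LY3471851 treatment groups each having 80 participants", and concludes that "a 17% or larger difference between the groups can be detected with 90% power and assuming a 5% placebo effect". It gives no alpha and no sidedness.

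The analysis sections take another line. Protocol 9.4.1, repeated in SAP 4.1.1, says that unless otherwise specified "analysis of hypotheses will be tested without multiplicity control at a significance level of 0.05", with two-sided 95% intervals. Protocol 9.4.1.3 says "Adjustment for multiple comparisons will not be employed in the analysis for this study" and SAP 2.1 says "Multiplicity adjustment will not be employed in the analysis for this study". SAP 4.3.2 calls a dose superior to placebo if its own pairwise p-value is below 0.05.

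**The concern.** The power paragraph and the analysis use different alphas, and the paragraph seems to change alpha part-way through. The three powers rest on 0.05/3. The example comes directly after that assumption, so a reader would carry 0.05/3 into it, yet its figure fits 0.05. The example also has 80 placebo patients where about 40 are planned.

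Two things are at stake. First, the printed powers are not those of the planned test, and the family-wise wording suggests an error control that the analysis does not provide. Second, power at the planned placebo size is given only for a 30-point difference. The only difference quoted at 90% power belongs to a design with twice the placebo patients. The study is meant to guide dose selection (Protocol 2.1), and its interim results feed termination, Stage 2 dose and Phase 3 decisions (SAP 4.8). If 17 points is taken as its sensitivity, a non-significant dose will look like stronger evidence against a moderate effect than it is.

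**Working it through.** **Inputs.** Placebo 5%, active 35%, active n = 40, 60 or 80, placebo n = 40, three tests at family-wise 0.05 (Protocol 9.2, SAP 5). Analysis alpha 0.05 per comparison (SAP 4.3.2). Two-sided is taken from Protocol 9.4.1 and SAP 4.1.1, because the sample-size sections do not state it. The example is 5% v 22% with 80 per group.

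**Formula (arcsine).** Power = Φ(h/√(1/n₁ + 1/n₀) − z), with h = 2·asin√p₁ − 2·asin√p₀. For 35% v 5%, h = 1.266 − 0.451 = 0.815. The two-sided z is 2.394 at 0.05/3 and 1.960 at 0.05.

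**Step 1: reproduce the stated powers, then move to the analysis alpha.**

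| Active v placebo | h/√(1/n₁+1/n₀) | Power at 0.05/3 | Stated | Power at 0.05 |
|---|---|---|---|---|
| 40 v 40 | 0.815/0.2236 = 3.645 | 89.5% | 89.5% | 95.4% |
| 60 v 40 | 0.815/0.2041 = 3.993 | 94.5% | 94.5% | 97.9% |
| 80 v 40 | 0.815/0.1936 = 4.209 | 96.5% | 96.5% | 98.8% |

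All three match to the printed decimal, so the plan used the arcsine formula at two-sided 0.05/3. At 0.05 the other formulas (unpooled, pooled, exact chi-square) give 95.1/93.4/95.6% for 40 active, 98.9/96.9/97.8% for 60 and 99.7/98.4/98.8% for 80.

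**Step 2: the 17-point example, 80 v 80.** For 22% v 5%, h = 0.976 − 0.451 = 0.525, and 0.525/0.1581 = 3.323.

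| Two-sided alpha | Power for 17 points: unpooled / arcsine / pooled / exact | 90%-power difference, same order (points) |
|---|---|---|
| 0.05 | 90 / 91 / 89 / 91% | 17.0 / 16.5 / 17.4 / 16.6 |
| 0.05/3 | 80 / 82 / 78 / 81% | 19.9 / 19.4 / 20.6 / 19.6 |

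The example fits 0.05 and not 0.05/3. One-sided 0.05/3 by arcsine comes close, at 88.4%. But that choice would make the three stated powers 93.5/96.9/98.1%, which is not what is printed, and the documents' inference is two-sided.

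**Step 3: the planned 40 placebo patients.** By arcsine, the h needed for 90% power is (z + 1.2816)·√(1/n₁ + 1/40). For 40 active at 0.05 that is 3.2416 × 0.2236 = 0.725. The active rate is then sin²((0.451 + 0.725)/2) = 30.8%, a difference of 25.8 points.

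| Active (40 placebo) | Power for 17 points at 0.05 | 90%-power difference at 0.05 (points) | Same at 0.05/3 (points) |
|---|---|---|---|
| 40 | 63 / 65 / 61 / 66% | 26.3 / 25.8 / 27.6 / 25.7 | 30.6 / 30.3 / 32.7 / 31.0 |
| 60 | 76 / 73 / 66 / 68% | 21.6 / 22.9 / 24.7 / 23.6 | 25.2 / 26.9 / 29.5 / 28.5 |
| 80 | 84 / 77 / 70 / 72% | 19.1 / 21.4 / 23.1 / 22.3 | 22.3 / 25.2 / 27.7 / 26.3 |

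The order is again unpooled / arcsine / pooled / exact. No formula reaches 17 points at 90% power.

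**Step 4: could placebo reach 80?** Stage 1 at 2:2:1 puts about 100 × 1/5 = 20 patients on placebo. Reaching 80 would take 60 of the roughly 100 Stage 2 patients, against a stated plan of about 40 in total.

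**The case against.** The plan's arithmetic is correct for the settings behind it. Planning at a stricter alpha than the test will use is safe. The paragraph itself calls the adjustment conservative, and both documents say elsewhere that the analysis is unadjusted. The example is openly labelled a fixed design and prints both group sizes, with the planned 40 placebo a few lines above. A default alpha of 0.05 exists, and the example fits it. The powered hypothesis is 35% v 5%, so a 90%-power difference is not a design target. Replacement figures would also be approximate. They ignore the four CMH factors (2 × 2 × 2 × 3 = up to 24 cells), the Stage 2 ratio is undecided, doses may change, and the formula alone moves the 80-active figure from 19.1 to 23.1 points.

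Much of this stands. The printed numbers are not miscalculated, the mismatch in the three powers is conservative, and the replacements should name their formula or be given as ranges. It does not remove the point. Neither sample-size section says that the analysis drops the Bonferroni adjustment. The example's alpha has to be inferred against the assumption just before it. The fixed-design label does not tell the reader that every planned arm needs a larger difference than 17 points.

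**Conclusion.** The concern holds as a fault in how design properties are stated, not in the size of the trial. Power for 35% v 5% under the planned test is 95.4/97.9/98.8% by arcsine (93-96, 97-99 and 98-100% across the four formulas), against 89.5/94.5/96.5% printed. The 17-point figure belongs to two-sided 0.05 with 80 placebo patients. With 40 placebo at 0.05, a true 17-point difference has 61-66%, 66-76% and 70-84% power for 40, 60 and 80 active, and 90% power needs 26-28, 22-25 and 19-23 points. This should be corrected, but it does not threaten the sample size.

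The figures assume a 5% placebo rate, two-sided tests and the approximate group sizes in the plan. They are unstratified and do not model interim dose selection.

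**What to change.** In Protocol 9.2 and SAP Section 5:

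1. State power at the analysis alpha: 95.4%, 97.9% and 98.8% for 40, 60 and 80 active v 40 placebo (arcsine, two-sided 0.05). Then either remove the Bonferroni and family-wise wording, or keep 89.5/94.5/96.5% labelled as a deliberate planning margin at 0.05/3 that the analysis does not use.
2. Replace or supplement the 17-point example with the 90%-power difference at 40 placebo: about 26, 23 and 21 points for 40, 60 and 80 active (arcsine, two-sided 0.05; 26-28, 22-25 and 19-23 across formulas).
3. If the 80 v 80 example stays, add that it uses two-sided alpha 0.05 with no multiplicity adjustment.

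SAP 2.1 needs no change. The cost is wording in two sections; the sample size, tests, alpha and success criterion are untouched. The stated power rises, and the stated detectable difference becomes less favourable.
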